- d. For multi-site studies for which the Yale PI serves as the lead investigator: n/a

The treatment interventions and assessment protocols are well-established and pose primarily low risks to participants. The DSMP for the proposed pilot RCT focuses on close monitoring by the PI in conjunction with an independent Safety Monitor. Excessive adverse events and/or any serious events (should they occur) will be reported promptly to the NIH and to the Yale School of Medicine IRB (Human Investigation Committee). Other (less serious) adverse events will be reported to the IRB periodically during regular reporting periods. In addition to the DSMP, the Yale IRB reviews all aspects of the study protocol (including progress and problems) minimally once per year.

Monitoring for the safety of participants and the integrity and quality of data will be the responsibility of the PI, the study team, and the Yale IRB (Human Investigation Committee).

The PI will be responsible for monitoring the safety of participants and the integrity and quality of data for the proposed pilot RCT, executing the DSMP, and complying with reporting requirements to the NIH and Yale IRB.

Qualifications and responsibilities of the Safety Monitor.

The Safety Monitor for this trial will be [name], MD, MPH. [name] is an Assistant Professor of Pediatrics in the section of General Pediatrics at Yale, and practices as a general pediatrician at the Yale Pediatric Primary Care Center. [name] is an experienced pediatrician with substantial clinical research and clinical expertise with adolescents and families, including those with obesity. [name] is not involved in the study design or clinical intervention or

related to any chain of command. As Safety Monitor, [name] will review the reports sent by the PI and will determine whether there is any corrective action, trigger of an ad hoc review, or stopping rule violation that should be communicated to the study PI, the IRB at the Yale School of Medicine, and the NIH.

Risk Assessment

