Data on adverse events will be collected on an ongoing basis. Adverse events data will be monitored by the PI and reviewed with the Safety Monitor throughout the pilot RCT (see Table above).

This protocol presents minimal risks to the subjects and Unanticipated Problems Involving Risks to Subjects or Others (UPIRSOs), including adverse events, are not anticipated. In the unlikely event that such problems occur, Reportable Events (which are events that are serious or life-threatening and unanticipated (or anticipated but occurring with a greater frequency than expected) and possibly, probably, or definitely related) or UPIRSOs that may require a temporary or permanent interruption of study activities will be reported immediately (if possible), followed by a written report within 5 calendar days of the PI becoming aware of the event to the IRB. The PI will apprise study personnel of all UPIRSOs and adverse events that occur during the conduct of this research project through regular study meetings, and via email as they are reviewed by the PI.

Attribution of Adverse Events:

Adverse events will be monitored for each subject participating in the study and attributed to the study procedures by the PI according to the following categories:

- a) Definite: Adverse event is clearly related to the study treatment or assessment procedure.
- b) Probable: Adverse event is likely related to the study treatment or assessment procedure.
- c) Possible: Adverse event may be related to the study treatment or assessment procedure.
- d) Unlikely: Adverse event is likely not to be related to the study treatment or assessment procedure.
- e) Unrelated: Adverse event is clearly not related to the study treatment or assessment procedure.

Plan for Grading Adverse Events:

The following scale will be used to grade the severity of adverse events (should they occur) during the study:

- a) Mild adverse event
- b) Moderate adverse event
- c) Severe adverse event

Plan for Determining Seriousness of Adverse Events:

In addition to grading adverse events, the PI will determine whether the adverse event meets the criteria for a Serious Adverse Event (SAE). An adverse event will be considered serious if it results in any of the following outcomes:

- a) Death;
- b) A life-threatening experience that results in in-patient hospitalization;
- c) A persistent or significant disability or incapacity;
- d) A congenital anomaly or birth defect; or

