- e) Any other adverse event that, based upon appropriate medical judgment, may jeopardize the subject's health and may require medical or surgical intervention to prevent one of the other outcomes listed in this definition.

Plan for reporting events to the Yale IRB that are unexpected AND related AND involve risk of harm to subjects or others:

The PI will report to the IRB any incident, experience or outcome that meets ALL 3 of the following criteria:

- 1) Is unexpected (in terms of nature, specificity, severity, or frequency) given (a) the research procedures described in the protocol-related documents, such as the IRB-approved protocol and informed consent document and (b) the characteristics of the subject population being studied; and
- 2) Is related or possibly related to participation in the research (possibly related means there is a reasonable possibility that the incident, experience, or outcome may have been caused by the procedures involved in the research); and
- 3) Suggests that the research places subjects or others at greater risk of harm (including physical, psychological, economic, legal, or social harm) than was previously known or recognized.

Unanticipated Problems Involving Risks to Subjects or Others (UPIRSOs) may be medical or non-medical in nature, and include – but are not limited to – serious, unexpected, and related adverse events.

All related events involving risk but not meeting the prompt reporting requirements described above will be reported to the IRB in summary form at the time of continuing review. If appropriate, such summary may be a simple brief statement that events have occurred at the expected frequency and level of severity as previously documented.

Plan for reporting adverse events to the mentors, Safety Monitor, study team, and funding agency:
For the current study, the following individuals, funding, and/or regulatory agencies will be notified:

- Primary Mentor ([name]) and Co-Mentor ([name]);
- All Co-Investigators listed on the protocol; and
- National Institutes of Health.

The PI will review all adverse events upon completion of every study subject. The PI will evaluate the frequency and severity of adverse events and determine if modifications to the protocol or consent form are required.

Procedures for providing follow up care:

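### The adverse event notification list omits the Safety Monitor named in its own heading, and serious-event criterion (b) covers life-threatening events and in-patient admission only in combination

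*Combined protocol and SAP*

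**What the plan says.** All the relevant text is in Section I, item 12 (Data and Safety Monitoring Plan, DSMP).

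**Notification.** One heading reads "Plan for reporting adverse events to the mentors, Safety Monitor, study team, and funding agency". Beneath it the plan states that "the following individuals, funding, and/or regulatory agencies will be notified", and lists the primary mentor and co-mentor, all co-investigators, and NIH. The opening of the DSMP describes "close monitoring by the PI in conjunction with an independent Safety Monitor". Under the Safety Monitor's qualifications and responsibilities, that person works from reports sent by the PI and decides whether corrective action, an ad hoc review or a stopping-rule violation must be communicated. The part on data integrity and quality gives the PI, the IRB and the Safety Monitor the power to stop or suspend the study. Measurement and Reporting of Adverse Events adds that the PI reviews adverse event data with the Safety Monitor over the course of the pilot RCT, and refers back to the review-frequency table. Row 4 of that table gives as-needed review by the PI, and annual review by the PI and Safety Monitor together.

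**Seriousness.** An event is serious if it meets any one of five items, (a) to (e). Item (b) is "A life-threatening experience that results in in-patient hospitalization". Item (e) rests on medical judgment and covers events that may endanger health and "may require medical or surgical intervention to prevent one of the other outcomes listed in this definition". Reportable Events are those "which are events that are serious or life-threatening and unanticipated" (or anticipated but more frequent than expected) that are also at least possibly related; a written report goes to the IRB within 5 calendar days. The opening of the DSMP says "Excessive adverse events and/or any serious events (should they occur) will be reported promptly to the NIH" and to the Yale IRB, whereas "Other (less serious) adverse events will be reported to the IRB periodically during regular reporting periods".

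**The concern.** The notification list does not do what its heading says. If staff follow the list, the one independent person in the monitoring plan is not told of individual adverse events, while everyone else named in the heading is. Participation lasts 7 months (4 of treatment, 3 of follow-up). A participant could therefore enroll, have a serious event and finish between two annual reviews.

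The wording of (b) matters because the serious label decides how fast an event is reported. Joining two conditions in one item leaves no item for an event that meets only one of them. The case is foreseeable in this trial: the DSMP's follow-up care text anticipates depressive symptoms or suicidality during the study and connection to a local emergency department. An admission could follow such a contact without being judged life-threatening.

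**Working it through.** The plan states no figure to reproduce, so the check compares passages.

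**Step 1. Heading against list.**

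| Recipient in the heading | In the list? |
|---|---|
| Mentors | Yes, primary mentor and co-mentor |
| Study team | Yes, as co-investigators |
| Funding agency | Yes, as NIH |
| Safety Monitor | No |

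Three of four match. Removal of personal names does not explain the gap, because role labels are kept in the list. Nor does another entry cover the role: the Safety Monitor is described as outside the design, the intervention and the chain of command.

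**Step 2. Does other text fill that gap?** The sentence on review throughout the pilot RCT helps in principle, but it defers to the table, and the table says annual. Earlier contact depends on the PI sending a report, or on a concern being raised under the general provision at the end of the treatment-completion part. The only scheduled Safety Monitor review of adverse events is therefore every 12 months, against a 7-month participation.

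**Step 3. Criterion (b) as a logical rule**, leaving aside events already serious under (a), (c) or (d).

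| Life-threatening | Admitted | Status |
|---|---|---|
| Yes | Yes | Serious under (b) |
| Yes | No | Not under (b); serious only through (e) |
| No | Yes | Not under (b); serious only through (e) |

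**Step 4. Follow the two unlisted rows through the reporting routes.**

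- *Life-threatening, not admitted.* Criterion (e) readily applies, since such an event may need intervention to prevent death, which is outcome (a). Separately, if it is unanticipated (or more frequent than expected) and at least possibly related, it reaches the IRB as a Reportable Event whether or not it is labeled serious. Most such events are covered.
- *Admitted, not life-threatening.* Criterion (e) applies only if the PI judges that intervention may be needed to prevent another listed outcome, and admission alone is not one of those. If (e) is not invoked, the event is neither serious nor life-threatening, so the Reportable Event rule does not apply. The separate IRB rule still catches it if it is unexpected, related or possibly related, and suggests greater risk than was known. If it is judged unrelated or expected, it fails that rule too and falls into periodic reporting.

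**Step 5. What is lost in that last case.** The event moves from prompt to periodic IRB reporting and out of the serious-event count. It stays in the adverse event data, because row 4 of the table covers adverse as well as serious adverse event rates.

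**The case against.** The strongest case is that both points are small and partly answered by the plan itself.

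- *The omission looks clerical.* The heading shows that notice to the Safety Monitor was intended, and the adverse event text has the data reviewed with that person during the trial. A reader might infer that the Safety Monitor is cut off from adverse event data. The documents do not support that: the annual review stands, and ad hoc contact is possible. What stands is that the list, taken literally, does not carry out its heading.
- *The Reportable Event wording need not contradict (b).* A reader might infer a direct conflict. The added life-threatening alternative can equally be read as complementing (b), by bringing in events that (b) leaves out. That is fair, and the wording says nothing about admission alone. Nothing in the documents states that an admission must count as serious in itself, so the point on admission is a request to state the intent.
- *Criterion (e) is broad, and all seriousness decisions involve judgment.* This stands for life-threatening events. A reader might also infer from the step 3 table that two-thirds of events escape the definition. The rows are drafting categories without weights and measure no frequency.
- *The prompt-reporting sentence does not cite the five-item definition.* True. Taking its serious events to be those meeting (a) to (e) is a natural reading, but it is an assumption.
- *Other oversight remains.* The PI monitors adverse events on an ongoing basis, safety is reported to the PI at all visits, and serious events go promptly to NIH and the IRB. All of this stands and limits the consequence.

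**Conclusion.** Both defects are present in the text and worth correcting. The notification gap is the clearer one: 1 of the 4 recipient groups in the heading is missing, and it is the independent role with authority to stop the study, whose only scheduled adverse event review is annual. The gap in (b) is narrower. It mainly concerns an admission not judged life-threatening, not placed under (e), and judged unrelated or expected; its IRB reporting becomes periodic, though it is still recorded and reviewed as an adverse event. This rests on reading the prompt-reporting rule as using the plan's own definition of serious. How many events would be affected cannot be estimated, because the documents give no event rate. The findings concern safety reporting only.

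**What to change.** 1. Add the Safety Monitor to the notification list so that it matches its heading.
2. Reconcile criterion (b) with the Reportable Event wording, and state explicitly whether a life-threatening event and an in-patient admission each count as serious on their own.

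Two further clarifications go beyond the defects and are optional: a timeline for notice to the Safety Monitor, and a statement of whether the prompt-reporting rule for any serious event applies in addition to the narrower IRB criteria.

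The cost is a wording amendment to the DSMP and perhaps a few extra reports to a Safety Monitor already in place. The aims, sample size and analysis do not change.

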“Focus interviews” will be conducted with adolescents and their parents based on the method described by Shea et al (57). Briefly, participants will be given a copy of “Overcoming Binge Eating,” a book that describes cognitive-behavioral therapy for binge eating in a self-help format, and then will be interviewed by a research clinician about the aspects of the treatment that they believe would work well for adolescents and the aspects of the treatment that they believe need to be adapted. Focus interviews will be recorded and transcribed. Participants who complete the focus interviews will have the option of participating in the “open series” of patients (see below) but will not be eligible for the RCT.

Treatment (see “adolescent treatment,” below) will be conducted with an open series of patients (N=5) to elaborate and refine the manual. Patients enrolled in the treatment-development phase will all receive active treatment. Patients and their parents will be asked to provide feedback about the new adolescent CBT in semi-structured interviews. Open-ended questions will explore preferences, acceptability of session content, and perceived benefits and costs to treatment parameters. Feedback from patients will refine protocols.

Initial Efficacy Testing. CBT for adolescent binge/LOC eating will be piloted with N=50 adolescents (randomly assigned to CBT n=25, or control n=25). Research clinicians with doctoral training in psychology will administer CBT and control conditions under the supervision of the PI. To demonstrate treatment acceptability (sessions attended; retention; patient/clinician ratings), feasibility, and efficacy, parents *and* adolescents will complete assessments (baseline, Month 1,

Month 2, Month 3, post, 3 month follow-up) for CBT and control conditions.

Format and Content of Treatment. The 16-session treatment (4 months; weekly sessions) will be delivered by research clinicians with doctoral training in psychology, supervised by the PI. Participants will be audio-recorded if they consent to this procedure. Audio recordings will be for the purpose of evaluating treatment fidelity, as well as part of monitoring research-clinicians in the delivery of the treatment as specified in the protocol.

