Adolescent Treatment. Adolescent therapy (see table) will have five stages and will occur during both the treatment-development and RCT phases of the study: 1) Orienting to treatment and establishing a therapeutic foundation; 2) Specific behavioral strategies and their implementation; 3) Coping skills training and implementation; 4) Integrated executive function skills; and 5) Relapse prevention planning to maintain health behaviors. As in general adolescent therapy (58), parents will have some involvement in therapy but the focus will be on adolescents. Parents will attend sessions monthly, during which they will learn about binge/LOC eating, collaborate to enhance adolescent awareness, identify parent and family factors that could inhibit change, and help the adolescent establish behavioral strategies that maximize improvement. Adolescents will teach parents what they have learned to increase self-efficacy and positive communication. Other developmentally-tailored content includes using tangible therapeutic tools, setting communication strategies and boundaries with parents, eliciting peer support and parent health-behavior support, and focus on both short- and long-term health goals. Executive function techniques will be taught as skills to reduce impulsivity, increase behavioral inhibition, improve planning, and promote long-term benefits in the context of health decision making, as has been done in anorexia nervosa treatment research (59-61). Executive function skills are expected to enhance therapeutic gains from behavioral and coping strategies.

Active Control. The control condition (see table) will address eating behaviors and nutrition, thereby having face validity and broad clinical appeal. The active control will be 4 months with mailed publicly-available information (weekly to match CBT; e.g., USDA healthy recipes, list of local recreation areas and activities) and monthly assessments (parent and adolescent attendance will be matched to CBT).

TABLE 1: CBT for adolescent binge/LOC eating and control conditions

Week	CBT for Adolescents	Control Condition
1	Orient to treatment: Establish collaborative therapeutic relationship with adolescent and parent cooperation; Educate adolescent and parent about binge/LOC eating	Orient to treatment: Establish collaborative relationship with adolescent and parent; Explain program format

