2. Has a medical or psychiatric condition that would prohibit them from engaging in behavioral treatment or moderate physical activity (e.g., cardiovascular problems);
3. Has uncontrolled medical condition(s) (e.g., uncontrolled diabetes or hypertension);
4. Is pregnant or breastfeeding;
5. Is taking medication(s) or participating in treatment(s) that could influence weight or appetite;
6. Began taking hormonal contraceptives less than 3 months prior;
7. Has a developmental or cognitive disorder (e.g., autism spectrum disorder);
8. Has a concurrent feeding/eating disorder (e.g., bulimia nervosa); or
9. Is participating in another clinical research study.

9. How will **eligibility** be determined, and by whom?

Participants will be interviewed during an initial intake by a study clinician. The semi-structured investigator-based Eating Disorder Examination (EDE) interview (child version) will be used to determine binge/LOC eating episodes and to characterize eating-disorder psychopathology. The EDE along with the MINI psychiatric interview will also determine whether participants have any co-existing psychiatric conditions that require referrals, hospitalization or more intensive/different treatment.

Final determination of eligibility will be from the PI.

10. **Risks:** Describe the reasonably foreseeable risks, including risks to subject privacy, discomforts, or inconveniences associated with subjects participating in the research.

The primary risks of the treatment development research and pilot RCT are the behavioral interventions, the assessment procedures, and unknown treatment efficacy.

Cognitive-behavioral therapy (CBT) is an established treatment for psychiatric conditions and health behavior change. CBT is established and widely-used in research and clinical settings, for both youth and adults. The only foreseeable risks include some mild discomfort or embarrassment when discussing eating patterns, weight, or body image concerns. Previous controlled clinical trials conducted by the PI and study team with similar interventions with adult and adolescent participants have not reported problems. Any troublesome effects would be readily identifiable by the experienced study clinicians during repeated evaluations. Thus, the risks of the CBT interventions are judged to be minimal.

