Research assessments are noninvasive and should add no substantial risk. The major disadvantages are the time taken to complete them and potential for a breach of confidentiality. Completion of the assessment interviews and surveys may cause some mild anxiety or embarrassment to some participants. Past experiences of the PI and study team indicate that the measures are acceptable to participants. Careful efforts aimed at maintaining confidentiality will be made (as described below).

There is a chance that participants' eating concerns and overweight may fail to improve or may worsen during the study. Participants will be withdrawn from the study if their clinical condition deteriorates to a significant degree, and they will be provided with appropriate referrals.

11. Minimizing Risks: Describe the manner in which the above-mentioned risks will be minimized.

The study clinicians will be carefully trained and supervised by the PI. All study clinicians and study staff will have IRB and ethics training; because of their educational experience and training (e.g., in psychology), they can reasonably be expected to identify potential problems and to take appropriate action as medically indicated. The PI will be continuously available to the study clinicians to discuss any problems and to implement any needed interventions or offer appropriate referrals. The detailed assessments repeated during the course of treatment will allow for additional and ample opportunity to identify difficulties. In the event that a participant experiences undue distress, resources are available. If a study participant experiences any psychiatric symptoms or distress (e.g., depressive symptoms or suicidality) at any stage of study participation they will receive short-term treatment and support from the PI and study treatment team (which includes psychologists) and will be connected with a local emergency department and their physician or a therapist for ongoing care.

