Study participant safety will be monitored by the study team and reported to the PI at all visits and referrals will be provided if warranted and/or requested. If a study participant experiences any psychiatric symptoms or distress (e.g., depressive symptoms or suicidality) at any stage of study participation they will receive short-term treatment and support from the study treatment team (which includes psychologists) and will be connected to a local emergency department and their physician or therapist for ongoing care.

Other Potential Issues Relating to Stopping Rules for the Pilot RCT Include:

- 1) **New Information:** It is unlikely that any new information would become available during this trial that would necessitate stopping the trial. If new data become available, these will be evaluated.
- 2) **Limits of Assumptions:** It is possible that baseline differences between the treatment conditions, excessive attrition, and/or missing data could limit the value of data analysis. Baseline differences across treatment groups, if present, will be evaluated twice yearly and considered in relation to potential effects on the power to detect differences in the primary outcomes. If these effects were to develop and be sizeable, alterations to the randomization schedule would be considered. Any plans to alter the randomization scheme would be communicated to the NIH.
- 3) **Limits of Rules:** There are other situations that could occur that might warrant stopping the trial and/or including a section on the safety report entitled “Other situations that have occurred since the last safety report that warrant discussion” to allow for communication of concerns.

13. **Statistical Considerations:** Describe the statistical analyses that support the study design.

DATA ANALYSIS AND AIMS

Baseline demographic and clinical characteristics will be compared between treatment and control groups using chi-square tests for categorical variables (e.g., sex) and ANOVAs or Kruskal-Wallis tests for continuous variables (e.g., BMI z-score). Continuous variables will be examined for adherence to normality using probability plots and Kolmogorov-Smirnov tests. If normality is not satisfied and transformations do not achieve acceptable normality, alternative strategies (e.g., nonparametric) will be considered. Dropouts and completers will also be compared. Analyses will be intent-to-treat. Outcomes will be tested at the $\alpha=0.05$ threshold.

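### Safety monitoring is tied to visits, CBT appears to have about 2.7 to 5 times as many contacts as control, and no common adverse event questions are scheduled at the shared assessments

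*Combined protocol and SAP*

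**What the plan says.** Section I, item 12, under *Procedures for providing follow up care*, states: "Study participant safety will be monitored by the study team and reported to the PI at all visits". Under *Measurement and Reporting of Adverse Events*, the same item describes collection as continuous and has the PI attribute, grade and classify each event. Neither place gives an elicitation question, a form, a schedule or a recall period. Event rates go to the PI as needed and to the PI and Safety Monitor annually.

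Contact is described in Section I, item 4. For CBT: "The 16-session treatment (4 months; weekly sessions) will be delivered by research clinicians with doctoral training in psychology". For control: "The active control will be 4 months with mailed publicly-available information (weekly to match CBT", together with "monthly assessments (parent and adolescent attendance will be matched to CBT". *Initial Efficacy Testing* adds: "Research clinicians with doctoral training in psychology will administer CBT and control conditions under the supervision of the PI". Table 1 lists a control orientation in week 1 and a completion celebration in week 16.

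Table 2 applies to both arms. The EDE interview is at baseline and post, and the MINI at baseline. The adolescent PHQ-9, EDE-Q, QEWP-5 and BMI-z are collected at baseline, Months 1, 2 and 3, Post and Follow-up. There is no adverse event row.

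The risk sections rely on this contact. Item 10 says: "Any troublesome effects would be readily identifiable by the experienced study clinicians during repeated evaluations". Item 11 says: "The detailed assessments repeated during the course of treatment will allow for additional and ample opportunity to identify difficulties".

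**The concern.** If safety is observed at visits, the number of visits governs how many events are recorded. Here the number of visits is part of what is randomized: one arm has weekly therapy, and the other mainly receives mail between monthly assessments. At equal true risk, the arm seen more often will tend to record more events.

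The protocol uses event frequency in several places. Anticipated events become reportable when they occur more often than expected, the PI weighs frequency and severity when deciding on protocol or consent changes, and rates go to the Safety Monitor. These uses are affected even with the arms pooled. Withdrawal for deterioration (item 10) and the support and referral pathway (items 11 and 12) also depend on someone noticing a problem. A later harms table by arm, which readers of a two-arm pilot would expect, would carry the imbalance forward.

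**Working it through.** The documents state no adverse event rate, detection rate or safety power, so there is no figure to reproduce. The check is a count of contacts, followed by an illustration of what the count could do.

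**Scheduled contacts after baseline, up to and including post (item 4, Tables 1 and 2)**

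- CBT: 16 sessions. There are four assessments (Months 1, 2, 3 and Post). If they fall on session days, the total is 16; if separate, 16 + 4 = 20.
- Control: four assessments = 4. If the week 1 orientation and week 16 celebration are additional visits, 4 + 2 = 6.
- Ratio: lowest 16/6 = 2.7; central 16/4 = 4; highest 20/4 = 5.
- With 25 per arm, the central reading is 16 × 25 = 400 contacts against 4 × 25 = 100.
- If the control arm in fact attends weekly, the ratio is 1.

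**Illustration 1 (assumed): an event is noticed only if a contact falls while it lasts**

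For an event lasting L weeks and a gap of g weeks between contacts, detection = min(1, L/g). Take g = 1 for CBT and g = 4 to 4.33 for control.

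| Event length | CBT | Control |
|---|---|---|
| 1 week | 100% | 23–25% |
| 2 weeks | 100% | 46–50% |
| 3 weeks | 100% | 69–75% |
| 4 weeks | 100% | 92–100% |
| 6 weeks | 100% | 100% |

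With an assumed true incidence of 20% in each arm, 0.20 × 25 = 5 events occur per arm. CBT would record 5. Control would record 5 × 0.25 = 1.25 if events last one week, and 5 × 0.50 = 2.5 if they last two (four-week gap).

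**Illustration 2 (assumed): every contact asks, but recall fades**

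Suppose 90% of events from the past week are reported and this halves for each further week. Weekly contact captures 90%. Monthly contact captures (0.90 + 0.45 + 0.225 + 0.1125)/4 = 0.42. The apparent rate ratio at equal true risk is 0.90/0.42 = 2.1.

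**Bounds**

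With complete recall over the whole interval, both arms capture everything and the ratio is 1. The largest distortion in these illustrations is the one-week event noticed only while present: 1/0.25 = 4 to 1/0.231 = 4.3.

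**What does not differ by arm**

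EDE and MINI timing is identical, as are the monthly questionnaires and weights and the three-month interval from post to follow-up. The difference comes from the therapy sessions alone.

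**The case against.** The strongest reply is that the protocol plans no comparison of adverse events by arm. Item 13 contains no harms endpoint, and the monitoring table lists rates without a breakdown. Where a between-arm safety look is intended, as for dropout, the protocol says so. This stands: the problem affects recorded frequencies and any later summary by arm, and contradicts no stated analysis.

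Second, a reader might infer that deterioration in control would surface only at post. The documents do not support that. Depressive symptoms, eating pathology and weight are each measured monthly in both arms, and items 10 and 11 present the repeated assessments as a means of finding problems. What remains is that nothing says who reads those scores for safety, or when.

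Third, a reader might take the lack of an interview between baseline and post as a weakness of the control arm. It applies equally to both arms and cannot by itself cause unequal ascertainment. Doctoral-level clinicians also administer the control condition, so its monthly contacts may involve one.

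Fourth, the protocol says attendance is matched. That cannot be called false; it is unexplained beside mailed content and monthly assessments. Collection is also described as continuous, so events may arrive outside visits, though no mechanism is given.

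Finally, the recall and duration figures are assumptions, and with 25 per arm a harms comparison would be imprecise even under equal ascertainment. Both points are fair. They limit the size that can be claimed and leave the direction of the bias unchanged.

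**Conclusion.** The point holds as a design weakness with an inexpensive remedy. As written, event capture depends on contact, and on the plain reading CBT has about 2.7 to 5 times as many scheduled contacts as control between baseline and post. Any summary of harms by arm would be potentially biased towards more events in CBT, and short-lived control events could be missed or found late.

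The size of the bias cannot be fixed from the documents. The illustrations run from no distortion (complete recall, or events of six weeks or more) to roughly fourfold (one-week events noticed only while present). The conclusion rests on control contact being monthly. If matched attendance means weekly visits, the contact imbalance disappears, leaving only the lack of a common question set and of a stated review of the monthly scores.

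The documents do not show that control deterioration would go undetected until post, or that a planned analysis is invalid.

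**What to change.** - Add one row to Table 2: a fixed adverse event question set, worded identically in both arms, at Months 1, 2, 3, Post and Follow-up, with a recall window running back to the previous assessment.
- State in the monitoring plan that any rates by arm use these time points only, and list events volunteered in CBT sessions separately. Those events still enter individual safety handling as now.
- State that existing study staff review each adolescent's monthly PHQ-9 and EDE-Q on receipt, in both arms, and pass concerns into the pathway already described in items 11 and 12. No new threshold is proposed here.
- Reconcile the matched-attendance wording under *Active Control* with the mailed content and monthly assessments, and say whether the week 1 and week 16 control entries in Table 1 are visits.

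The cost is wording in Table 2 and item 12, slightly longer assessments and a little existing staff time, with no new visits or staff. Acting on questionnaire scores could add some clinician contact in the control arm, which should be recorded. Recall over a month or more will still be incomplete, but the questions and the period they cover will be the same in both arms.
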